14.15 Injection Site Reaction Management

Table 23: Management Guidelines for Injection-Site Reactions

Grade	Management
Grade 1	
 Consider treatment with topical steroids. Continue mosunetuzumab in subsequent cycles.
Grade 2	
 Notify Principal Investigator. Initiate treatment with topical steroids. If progressive after 24 hours, consider prednisone or equivalent 10–30 mg/day. Continue mosunetuzumab in subsequent cycles after improvement to Grade ≤ 1.
Grade 3	
 Notify Principal Investigator. Withhold mosunetuzumab. Initiate prednisone 1 mg/kg/day or equivalent. Consult dermatology. Taper steroids after improvement to Grade ≤ 1. Continue mosunetuzumab in subsequent cycles after improvement to Grade ≤ 1.
Grade 4	
 Notify Principal Investigator. Management as for Grade 3. Permanently discontinue mosunetuzumab SC. Consider continuing study treatment with mosunetuzumab IV after discussion with Principal Investigator.

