4.3.1 Rationale for Dose Selection/Regimen/Modification

Mosunetuzumab

Mosunetuzumab monotherapy has been examined in relapsed/refractory B-cell NHL⁶ as well as untreated DLBCL in patients unfit for standard treatment²¹.

Subcutaneous mosunetuzumab has been tested in a phase 1/1b with both flat dosing as well as step-up dosing [Matasar, 2020 #1294]. In the flat dosing cohort, patients were treated at 1.6 to 20 mg dose cohorts in a standard 3+3 design. A single DLT was observed at 1.6 mg (grade 4 neutropenia). Escalation otherwise proceeded without any other DLTs observed in other cohorts, and 26 patients treated at the final 20 mg dose. All CRS events across all cohorts were grade 1 (n=6, 26%) and grade 2 (n=2, 9%) and occurred during cycle 1. Efficacy in relapsed/refractory indolent NHL

patients were similar to results seen in the previously presented intravenous cohorts.

To further reduce the rate and severity of CRS events, and to improve patient convenience, mosunetuzumab SC step-up dosing regimens of 5/15/45 mg (F1) and 5/45/45 mg (F2) are being evaluated in Study GO29781 Group F. The C1D1 dose of 5 mg SC was selected as the projected C_{max} is similar to 1 mg IV, the recommended initial dose of the IV step-up dosing regimen. This starting dose of 5 mg was within the range evaluated in the Group D flat dosing schedule. The target dose was selected at 45 mg SC, as it is projected to provide a lower C_{max} (population pharmacokinetics [popPK] model predicted geometric mean ratio [GMR] = 0.37) but higher AUC ([GMR] = 1.49) at steady state than the 30 mg IV maintenance dose. Therefore, it is expected to be associated with sufficient exposure to drive anti-tumor activity with a potentially lower risk of CRS compared with Mosunetuzumab IV 1/2/60/30 mg dosing. Two different doses (15 mg and 45 mg) were evaluated on C1D8 to further evaluate step-up dosing for CRS mitigation to reach the target dose of 45 mg. The 5/45/45 mg dosing regimen showed comparable safety profiles to the 5/15/45 mg dosing regimen but with a shortened window of CRS associated mostly with only the first two doses of mosunetuzumab during cycle 1. Further, the 5/45/45 mg dosing regimen also allows faster achievement of target dose. Therefore, this dose is considered the preferred dose for mosunetuzumab SC monotherapy.

Polatuzumab vedotin combinations in B-cell NHL

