5.3 Study Treatments

For the purposes of this protocol, Part A will refer to the subcutaneous (SC) mosunetuzumab monotherapy portion, while part B will refer to the polatuzumab vedotin and obinutuzumab combination portion.

Part A

The dosing of SC mosunetuzumab is listed in Table 2. Cycle length is 21 days. The rationale for this dosing is described in section 4.2.1. A step-up regimen will be employed to minimize the risk of CRS. Subjects will receive lower doses of the drug on cycle 1 day 1 and achieving the full dose on cycle 1 day 8. The full dose alone will be given on cycle 2 through 8 on day 1 only.

Table 2: SC mosunetuzumab dosing

	Cycle 1			Cycle 2-8
	Day 1	Day 8	Day 15	Day 1
Mosunetuzumab dose (SC)	5 mg	45 mg	45 mg	45 mg

Cycle length = 21 days

Subcutaneous mosunetuzumab will be prepared and administered according to appendix 14.15. Corticosteroids (dexamethasone 10 mg PO or equivalent) should be given pre-dose as well as 24 hours (+/- 4 hours) and 48 hours (+/- 4 hours) post dose during cycles 1 and 2. Oral acetaminophen (500-1000 mg) and/or diphenhydramine (25-50 mg) may also be administered per standard institutional practice prior to mosunetuzumab. Pre-medications from cycle 3 onward are optional provided that the patient did not have cytokine release syndrome during the previous cycle. Hydration and tumor lysis syndrome (TLS) prophylaxis is also at the discretion of the investigator. Corticosteroid administration in cycle 3 and beyond is up to the investigator. However, if a subject experiences CRS then corticosteroids should be administered for the subsequent doses until no CRS is observed.

For SC administration, mosunetuzumab will be administered by qualified staff over 30 seconds to 2 minutes. Refer to appendix 14.15 for more details including syringe size and preferred injection site. The recommended management of injection-site reactions is detailed in Appendix 14.14

Following each mosunetuzumab dose, patients will be observed at least 30 minutes for cycle 1 day 1 for fever, chills, rigors, hypotension, nausea, or other signs and symptoms of CRS. If tolerated during C1D1, subsequent observation times can be reduced to 15 minutes.

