14.16 Mosunetuzumab pharmacy preparation

PHARMACY INFORMATION

How mosunetuzumab is supplied: Mosunetuzumab for SC injection is provided as solution for injection Ro703-0816/F03-01 and Ro703-0816/F05-02 by Genentech, Inc.

Mosunetuzumab drug product in Formulation F03 is provided as a sterile, colorless to brownish yellow liquid solution and contains no preservatives. Each single dose, 2-mL vial contains 45 mg (net quantity) of mosunetuzumab, formulated with 45 mg/mL mosunetuzumab in a solution containing histidine, acetic acid, sucrose, polysorbate 20, and L- methionine, at pH 5.8.

Mosunetuzumab drug product in Formulation F05 is provided as a sterile, colorless to brownish liquid solution and contains no preservatives. Each single dose, 2-mL vial contains 5 mg (net quantity) of mosunetuzumab, formulated with 10 mg/mL mosunetuzumab in a solution containing histidine, acetic acid, sucrose, polysorbate 20, and L- methionine, at pH 5.8.

Storage: Mosunetuzumab (F03, F05) must be refrigerated at 2°C-8°C (36°F-46°F) until use.

Mosunetuzumab should not be used beyond the expiration date provided by the manufacturer. Vials should not be frozen or shaken and should be protected from light during storage.

Stability: If necessary, unopened mosunetuzumab vials may be stored at ambient temperature (8°C-25°C [46°F-77°F]) for up to 8 hours.

Route of administration: Subcutaneous. Intravenous formulations of mosunetuzumab are not used in this study.

Preparation of mosunetuzumab for SC. injection

Equipment

For preparation of the dose solution, polypropylene/polycarbonate, disposable sterile syringes with latex-free rubber components are recommended. Use an appropriately sized stainless steel needle (e.g. 21G 1" or 18G) for withdrawal, pooling, or transfer of the drug product.

Equipment needed:

- Stainless steel needles of 27G (or similar suitable gauge) are to be used for administration of dose solution.
- Perform pooling, transfer and administration of the study drug with polypropylene or polycarbonate disposable syringes with latex-free rubber components.

- Use polyethylene stoppers or polypropylene tip caps/syringe caps for sealing filled syringes to prevent evaporation if storage in syringe is required.
- Empty sterile glass vials may be used for pooling of drug product if required per site best practice.
- The smallest size syringe that can accurately deliver the injection volume should be used.

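### Table 23 offers intravenous mosunetuzumab after a grade 4 injection-site reaction, but Appendix 14.16 excludes the intravenous form from the study and the protocol gives no intravenous instruction

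*Combined protocol and SAP*

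**What the plan says.** Section 5.3 sends sites to an appendix for managing injection-site reactions. It cites 14.14, but the text stands at 14.15, as Table 23. The grade 4 row there asks for notification of the Principal Investigator and management as for grade 3. It then says "Permanently discontinue mosunetuzumab SC", followed by "Consider continuing study treatment with mosunetuzumab IV after discussion with Principal Investigator".

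Appendix 14.16, on pharmacy preparation, gives the route as subcutaneous and adds "Intravenous formulations of mosunetuzumab are not used in this study". On supply it says "Mosunetuzumab for SC injection is provided as solution for injection" and describes two vial formulations, F03 and F05, both prepared for subcutaneous use.

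Section 5.3 is consistent with 14.16. It states that "Part A will refer to the subcutaneous (SC) mosunetuzumab monotherapy portion", its dosing table is headed "Table 2: SC mosunetuzumab dosing", and its administration instruction reads "For SC administration, mosunetuzumab will be administered by qualified staff over 30 seconds to 2 minutes".

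Two further rules in Section 5.3 bear on the same event. Subjects who must stop mosunetuzumab monotherapy permanently because of toxicity are to have a PET/CT response assessment and be evaluated for Part B. And a grade 4 treatment-related non-hematologic event in general ends all study treatment, with no re-treatment.

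**The concern.** Table 23 is the instruction a site would open when this event occurs. It names a continuation route and calls it study treatment, so the line cannot be read as advice about care outside the protocol. The next appendix says the form needed for that route is not part of the study. A site that took up the option would find no dose, restart schedule or administration procedure for it in the protocol. Read together with Section 5.3, the site has three different onward paths for one grade 4 event and no statement of which takes precedence.

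What is at stake is consistent handling of a severe reaction, and a clear record of which treatment a subject received in a trial that sets out to evaluate subcutaneous mosunetuzumab.

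**Working it through.** No arithmetic applies. The check was to set every mention of mosunetuzumab route, supply, dosing, administration and monitoring side by side.

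| Place | Content relevant to a grade 4 injection-site reaction |
|---|---|
| Appendix 14.15, Table 23 | Subcutaneous drug stopped permanently; continuing study treatment intravenously may be considered after discussion with the Principal Investigator |
| Appendix 14.16 | Subcutaneous route; intravenous formulations not used; F03 and F05 described |
| Appendix 14.16, Tables 24 and 25 | Volumes for subcutaneous injection only |
| Section 5.3, Part A and Table 2 | Subcutaneous doses and subcutaneous administration only |
| Section 5.3, Part A, permanent discontinuation for toxicity | PET/CT, then evaluation for Part B |
| Section 5.3, mosunetuzumab toxicity management | Grade 4 related non-hematologic event: in general, all study treatment ends without re-treatment; the text then lets subjects who stop mosunetuzumab for toxicity enter Part B at investigator discretion |

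**Step 1: is the intravenous option excluded elsewhere?** Yes. The statement in Appendix 14.16 has no exception, and discussion with the Principal Investigator does not create one.

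**Step 2: is there an intravenous procedure somewhere else in the protocol?** Four places might seem to supply one.
- The trial summary lists both subcutaneous and intravenous routes. The two Part B drugs are intravenous, which explains the entry.
- Sections 4.3 and 4.3.1 mention intravenous mosunetuzumab regimens. These are results from other work, used to justify the subcutaneous dose.
- A footnote to the CRS table in Appendix 14.5 refers to a mosunetuzumab infusion. It gives no dose or procedure.
- Table 6 covers infusion reactions but is introduced for obinutuzumab, and Table 7 covers premedication for the Part B drugs.

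None of these is an instruction for giving mosunetuzumab intravenously in this trial.

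**Step 3: does the row fit the other two rules?** A grade 4 injection-site reaction would ordinarily be classed as treatment-related and non-hematologic (an inference, but a natural one). The general rule in Section 5.3 then points to ending all study treatment, the discontinuation paragraph points to evaluation for Part B, and Table 23 points to possible continuation of the same drug by another route. The words 'in general' leave room for exceptions, but neither place says that Table 23 is one.

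**The case against.** The best defence is that the Table 23 line only invites consideration. An investigator who considers the intravenous route, discusses it and declines has complied with both appendices. That stands: the accurate statement is that one appendix offers an option the other rules out, not that the two can never both be followed. It is also fair that an actual switch is unlikely, since 14.16 provides only subcutaneous product and the Principal Investigator must be consulted. This limits the consequences but does not remove the contradiction.

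A reader might infer that a switched patient would have no protocol safeguards. The documents do not support that. Post-dose observation in Section 5.3 applies after each mosunetuzumab dose, the requirement for a setting with immediate code-team access is not tied to a route, and the CRS table in Appendix 14.5 is not limited to subcutaneous dosing. What is missing is anything specific to the intravenous route. Section 5.3.1 also refers to the investigator brochure, which is not available here, so the absence is established for this document only.

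A reader might also use the exposure comparison in Section 4.3.1, "model predicted geometric mean ratio [GMR] = 0.37", to put a size on the rise in peak concentration after a switch. That ratio compares 45 mg subcutaneously with 30 mg intravenously at steady state. Table 23 names no intravenous dose, so the ratio cannot be carried over to this event.

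**Conclusion.** The inconsistency is real and plain on the text: Table 23 permits considering a route that Appendix 14.16 excludes and for which the protocol has no dose or route-specific instruction. The same row is also not aligned with the two Section 5.3 rules on grade 4 events and on permanent discontinuation for toxicity.

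Its size is minor. That a grade 4 injection-site reaction will be rare is an assumption (0 to 1 of 42 subjects); the protocol gives no rate. The event would count toward the Section 8.0 suspension rule for grade 4 treatment-related non-hematologic toxicity whichever path the site follows.

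A reader might infer that the primary complete response rate is threatened. The documents do not support making that a separate point. One subject is simply one of 42, the study is a pilot not sized to test a hypothesis, and best response by end of therapy already includes responses reached in Part B. Nor does Section 9.1 add to the conflict: it lists each product as a solution for injection and gives no route.

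The conclusion rests only on the wording of Appendices 14.15 and 14.16 and Section 5.3, and on none of these figures.

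**What to change.** Reconcile the grade 4 row of Table 23 with the route statement in Appendix 14.16, with the dosing and administration text of Section 5.3 (including Table 2), and with the Section 5.3 rules on grade 4 non-hematologic events and on permanent discontinuation for toxicity. After the change, a site opening any of these should find the same instruction for this event. Which rule is right is a clinical decision for the sponsor, and this review takes no position on it.

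The cross-reference in Section 5.3 to the injection-site appendix (cited as 14.14, located at 14.15) can be corrected in the same edit.

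The cost is a protocol wording amendment. Sample size, the 34 of 42 benchmark, the assessment schedule and the analysis in Section 8.0 are unaffected by removing the contradiction.

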14.16 Mosunetuzumab pharmacy preparation

PHARMACY INFORMATION

How mosunetuzumab is supplied: Mosunetuzumab for SC injection is provided as solution for injection Ro703-0816/F03-01 and Ro703-0816/F05-02 by Genentech, Inc.

Mosunetuzumab drug product in Formulation F03 is provided as a sterile, colorless to brownish yellow liquid solution and contains no preservatives. Each single dose, 2-mL vial contains 45 mg (net quantity) of mosunetuzumab, formulated with 45 mg/mL mosunetuzumab in a solution containing histidine, acetic acid, sucrose, polysorbate 20, and L- methionine, at pH 5.8.

Mosunetuzumab drug product in Formulation F05 is provided as a sterile, colorless to brownish liquid solution and contains no preservatives. Each single dose, 2-mL vial contains 5 mg (net quantity) of mosunetuzumab, formulated with 10 mg/mL mosunetuzumab in a solution containing histidine, acetic acid, sucrose, polysorbate 20, and L- methionine, at pH 5.8.

Storage: Mosunetuzumab (F03, F05) must be refrigerated at 2°C-8°C (36°F-46°F) until use.

Mosunetuzumab should not be used beyond the expiration date provided by the manufacturer. Vials should not be frozen or shaken and should be protected from light during storage.

Stability: If necessary, unopened mosunetuzumab vials may be stored at ambient temperature (8°C-25°C [46°F-77°F]) for up to 8 hours.

Route of administration: Subcutaneous. Intravenous formulations of mosunetuzumab are not used in this study.

Preparation of mosunetuzumab for SC. injection

Equipment

For preparation of the dose solution, polypropylene/polycarbonate, disposable sterile syringes with latex-free rubber components are recommended. Use an appropriately sized stainless steel needle (e.g. 21G 1" or 18G) for withdrawal, pooling, or transfer of the drug product.

Equipment needed:

- Stainless steel needles of 27G (or similar suitable gauge) are to be used for administration of dose solution.
- Perform pooling, transfer and administration of the study drug with polypropylene or polycarbonate disposable syringes with latex-free rubber components.

- Use polyethylene stoppers or polypropylene tip caps/syringe caps for sealing filled syringes to prevent evaporation if storage in syringe is required.
- Empty sterile glass vials may be used for pooling of drug product if required per site best practice.
- The smallest size syringe that can accurately deliver the injection volume should be used.
- When administered subcutaneously, mosunetuzumab will be delivered by medical syringe with a final mosunetuzumab volume not to exceed 2.0 mL.

Preparation

Dose preparation must occur under aseptic conditions, as the mosunetuzumab contains no preservatives.

- Visually inspect drug product solution for particulate matter and discoloration prior to dose solution preparation. Do not use the vial if the solution is cloudy, is discolored, or contains particulate matter.
- Each vial, Drug Product, or diluent, should be used for one dilution/one injection only. Partially used vials should NOT be re-used, they should be discarded immediately.
- The Drug Product, or diluent should be allowed to acclimate to room temperature for approximately 30 minutes prior to preparation for administration.

Perform manipulations of the study drug and diluent with standard disposable syringes and stainless steel needles. Always use the smallest syringe that will hold the required volume to manipulate solutions. For preparation of the dose solution, polypropylene/polycarbonate, disposable sterile syringes with latex-free rubber components are recommended. Stainless steel needles of 18 Gauge (G) are recommended for withdrawal of the investigational product.

Preparing the syringe for injection (F05 - 5 mg/0.5 mL or F03 - 45 mg/1 mL):

1. See Table 24 below for drug volumes for 5 mg/0.5 mL and Table 25 for 45 mg/1 mL.
2. Remove the plastic flip-off seal from drug product vial(s), and swab the top of the vial with an alcohol swab.
3. Place a transfer needle (19G x 1½" or 19G x 1.1" or 18G x 1½" or 18G) onto a Luer lock syringe (smallest size that can accurately deliver the dose) using aseptic technique.
4. Push the needle into the center of the vial stopper.
5. Withdraw study drug from the inverted vial.
6. Ensure that the plunger rod is drawn sufficiently back when emptying the vial in order to completely empty the needle. If pooling is required for the dose level, pool drug product per site best practices.
7. The transfer needle should be discarded after withdrawal of the vial contents and must not be used for the subcutaneous injection.
8. Attach a 27-gauge x ½-inch sterile injection needle (or similar needle suitable for subcutaneous injection) firmly onto the syringe by screwing it tightly onto the Luer lock. Carefully remove the needle cap by pulling it straight off. Do not wipe the needle at any time.

9. Hold the syringe with the needle pointing up. If there are any air bubbles, gently tap the syringe with your finger until the bubbles rise to the top.
10. Hold the syringe at eye level, and carefully push the plunger rod until the plunger tip is aligned with the line that marks the appropriate dose volume on the syringe.
11. Visually inspect drug product solution for particulate matter and discoloration after dose solution preparation. Do not use the syringe if the solution is cloudy, is discolored, or contains particulate matter.

Table 24: Study Drug (mosunetuzumab, F05, 5 mg/ 0.5mL) for Subcutaneous Injection

Dose level (mg)	Volume of study drug (mL)	Number of vials required	Administered volume (mL)
5.0	0.5	1	0.5
20.0	2.0	4	2.0
Above 20.0	Please use a 45 mg/1 mL vial volume		

Table 25: Study Drug (mosunetuzumab, F03, 45 mg/ 1mL) for Subcutaneous Injection

Dose level (mg)	Volume of study drug (mL)	Number of vials required	Administered volume (mL)
45.0	1.0	1	1.0

Do not shake or freeze syringes containing dose solution. Protect from direct sunlight (exposure to indoor ambient light is acceptable).

Mosunetuzumab must be prepared for dosing under appropriate aseptic conditions as it does not contain preservatives. The dose solution should be used immediately to limit microbial growth in case of potential accidental contamination.

If not used immediately, the dose solution in vial or syringe may be stored refrigerated at 2-8°C (36-46°F) for up to 24 hours prior to administration. The dose solution in vial or syringe may be temporarily held at 9-25°C (47-77°F) up to a maximum of 4 hours. The dose solution should be discarded if the cumulative storage time of the dose solution prior to administration exceeds 24 hours.

If the prepared dose solution is stored at 2-8°C (36-46°F), it should be removed from refrigeration and allowed to reach room temperature prior to administration.

The filled syringe without injection needle attached should be capped or stoppered (to prevent evaporation) and protected from direct sunlight if storage is required before administration.

Filled syringes with the injection needle already attached (either before or after adjusted to final volume) must be used immediately as the solution may dry and clog the injection needle.

14.17 Management of Neurologic toxicity including ICANS

Grade ^{a, b}	Actions
Grade 1	
 - Continue Mosunetuzumab and monitor neurologic toxicity symptoms. - If Grade 1 ICANS,^b consider a single dose of dexamethasone 10mg, if not taking other corticosteroids.
Grade 2	
 - Withhold Mosunetuzumab until neurologic toxicity symptoms improve to Grade 1 or baseline.^{c,d} - Provide supportive therapy and consider neurologic consultation and evaluation. - If Grade 2 ICANS,^b treat with dexamethasone 10 mg intravenously every 12 hours, if not taking other corticosteroids, until improvement to Grade 1, then taper.
Grade 3	
 - Withhold Mosunetuzumab until neurologic toxicity symptoms improve to Grade 1 or baseline for at least 7 days.^{d,e} - For Grade 3 neurologic events lasting more than 7 days, consider permanently discontinuing Mosunetuzumab. - Provide supportive therapy, which may include intensive care, and consider neurologic consultation and evaluation. - If Grade 3 ICANS,^b treat with dexamethasone 10 mg intravenously every 6 hours, if not taking other corticosteroids, until improvement to Grade 1, then taper. Consider non-sedating anti-seizure medication for seizure prophylaxis until resolution of ICANS. Use anti-seizure medication for seizure management as needed.
Grade 4	
 - Permanently discontinue Mosunetuzumab. - Provide supportive therapy, which may include intensive care, and consider neurologic consultation and evaluation. - If Grade 4 ICANS,^b treat with dexamethasone 10 mg intravenously every 6 hours, if not taking other corticosteroids, until improvement to Grade 1, then taper. Consider non-sedating anti-seizure medication for seizure prophylaxis until resolution of ICANS. Use anti-seizure medication for seizure management as needed.

a - Neurologic toxicity grading per National Cancer Institute Common Terminology Criteria for Adverse Events (NCI CTCAE).

b - American Society for Transplantation and Cellular Therapy (ASTCT) consensus grading criteria.

c - Consider the type of neurologic toxicity before deciding to withhold Mosunetuzumab.

d - See Delayed or Missed Doses for guidance on restarting Mosunetuzumab after dose delay.

e - Evaluate benefit/risk before restarting Mosunetuzumab.

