- For neutropenia, the ANC should resolve to Grade ≤ 2 or return to $\geq 80\%$ of the baseline value, whichever is lower.
- For increased lab values the abnormality should have resolved to the upper limit of Grade ≤ 1 , or return to $\leq 120\%$ of the baseline value, whichever is higher.

In the event that a patient has a toxicity in Cycle 1 necessitating mosunetuzumab interruption for >7 days, the Principal Investigator should be notified and the patient may be required to repeat mosunetuzumab at the highest dose previously tolerated prior to resuming the planned treatment schedule.

If scheduled dosing coincides with a holiday that precludes dosing, dosing should commence on the nearest following date, with subsequent dosing continuing on a 21-day schedule as applicable.

Patients who discontinue all study treatment for adverse events should continue to have disease assessments per institutional standard of care.

Additional guidance on the management of other risks that may be associated with mosunetuzumab is described in Appendix 14.9 (Neurologic AEs), Appendix 14.10 (Tumor Inflammation or flare), Appendix 14.11 (Neutropenia and thrombocytopenia), Appendix 14.12 (Infections) and Appendix 14.13 (Elevated Liver Enzymes).

Part B

For patients eligible for treatment in Part B, treatment will commence with cycle 9 day 1. This may be delayed for patients who require a washout of an agent listed in appendix 14.4. Cycle length is 21 days. Polatuzumab vedotin will be administered on day 1 of each cycle. Obinutuzumab 1000 mg will be administered (See table 5 and 6 for details on pre-medications and infusion related reaction management) on cycle 9 day 1, day 8, and day 15. From cycle 10 onwards obinutuzumab will only be administered on day 1 (1000 mg). Part B will be administered for 6 total cycles (through cycle 14). A response assessment by CT should be performed after cycle 11, and an end of treatment PET/CT should be performed after cycle 14. Obinutuzumab should be administered prior to polatuzumab vedotin on days that both drugs are administered.

Table 3: Part B dosing table

	Cycle 9			Cycle 10-14
	Day 1	Day 8	Day 15	Day 1
Obinutuzumab IV	1000 mg	1000 mg	1000 mg	1000 mg
Polatuzumab vedotin IV	1.8 mg/kg			1.8 mg/kg

Cycle length = 21 days

Dose Modification

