14.9 Table 16: Management Guidelines for Neurologic AEs for Patients Receiving Mosunetuzumab

Event	Grade	Management
-------	-------	------------

Seizure	Grade 1–2	
 • Withhold further study treatment; provide supportive care. • Consider treatment with corticosteroids. • Consider consultation with a neurologist; consider brain MRI, lumbar puncture, EEG. • Study treatment may be resumed with PI approval if no recurrent seizure for at least 3 days and with confirmation of baseline neurologic examination. a
	Grade 3–4	
 • Permanently discontinue study treatment; provide supportive care. • Consider treatment with corticosteroids. • Obtain neurology consultation.
Neurologic events not otherwise specified	Grade 1	
 • Notify PI. • Consider withholding study treatment during evaluation.
	Grade 2	
 • Notify PI. • Withhold mosunetuzumab and evaluate etiology. Consider imaging as appropriate. • Consider treatment with corticosteroids. • Consider neurology consultation. • Study treatment may be resumed when symptoms have returned to baseline ≥ 3 consecutive days without the need for medical management and with confirmation of baseline neurologic examination. a
	Grade 3	
 • Notify PI. • Withhold mosunetuzumab and evaluate etiology. Consider imaging as appropriate. • Consider treatment with corticosteroids. • Obtain neurology consultation. • Consider discontinuation mosunetuzumab if symptoms persist > 7 days. a • Mosunetuzumab may be resumed when symptoms have returned to baseline ≥ 3 consecutive days without the need for medical management and with baseline neurologic examination. • Permanently discontinue study treatment for recurrent Grade 3 event.

	Grade 4	
 • Notify PI. • Permanently discontinue mosunetuzumab. • Obtain neurology consultation.

MRI=magnetic resonance imaging.

^a The overall benefit–risk of continued treatment with mosunetuzumab should be assessed by the study investigator in consultation with and approval of the Principal Investigator.

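### Appendices 14.9 and 14.17 set different conditions for restarting mosunetuzumab after the same Grade 2 or Grade 3 neurologic event, and nothing says which prevails

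*Combined protocol and SAP*

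**What the plan says.** Appendix 14.9 (Table 16) has one block of rows for seizure and another for neurologic events not otherwise specified.

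- Grade 2, not otherwise specified: withhold. "Study treatment may be resumed when symptoms have returned to baseline ≥ 3 consecutive days without the need for medical management", with the baseline neurologic examination confirmed. A footnote asks for Principal Investigator approval of continued treatment.
- Grade 3, not otherwise specified: withhold. "Mosunetuzumab may be resumed when symptoms have returned to baseline ≥ 3 consecutive days without the need for medical management and with baseline neurologic examination". Also "Consider discontinuation mosunetuzumab if symptoms persist > 7 days", and "Permanently discontinue study treatment for recurrent Grade 3 event".
- Grade 3-4 seizure: "Permanently discontinue study treatment; provide supportive care".

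Appendix 14.17 also covers neurologic toxicity on mosunetuzumab by grade.

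- Grade 2: the hold lasts until symptoms reach Grade 1 or baseline, with no minimum time. A footnote lets the type of toxicity bear on whether to withhold at all.
- Grade 3: "Withhold Mosunetuzumab until neurologic toxicity symptoms improve to Grade 1 or baseline for at least 7 days". Permanent discontinuation is to be considered when the event lasts beyond 7 days, and a footnote asks for a benefit/risk evaluation before restart.

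Section 5.3 points the reader to one of the two: "Additional guidance on the management of other risks that may be associated with mosunetuzumab is described in Appendix 14.9 (Neurologic AEs". It does not cite 14.17, although the table of contents lists both appendices. Neither appendix refers to the other.

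**The concern.** Both tables answer the same question for the same patient: has this neurologic event recovered enough to give mosunetuzumab again? They differ on how far symptoms must recover, for how long, and whether a repeat event ends treatment. An investigator following one table can therefore re-dose, or withhold, contrary to the other.

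What is at stake is first the safety of re-dosing after neurotoxicity. Second, under Section 5.3 a permanent stop of mosunetuzumab for toxicity leads to an early PET/CT and possible entry to Part B. The stopping rule applied could therefore affect exposure and who falls into each group of the exploratory split in Section 3.0 (mosunetuzumab alone versus mosunetuzumab followed by Part B).

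**Working it through.** The plan gives no figure to reproduce here. The check sets the two tables side by side and then runs cases through both.

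**Do they cover the same events?** Yes. The title of 14.17 says it includes ICANS, which does not limit it to ICANS. Its first footnote grades neurologic toxicity by CTCAE, and ICANS appears only as a conditional item within each grade. Table 16 covers seizure and all other neurologic events.

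| Item | 14.9, Table 16 | 14.17 |
|---|---|---|
| Grade 2 (non-seizure): recovery level | Baseline, examination confirmed | Grade 1 or baseline |
| Grade 2 (non-seizure): minimum time | 3 consecutive days, no medical management | None |
| Grade 3 (non-seizure): recovery level | Baseline, with baseline examination | Grade 1 or baseline |
| Grade 3 (non-seizure): minimum time | 3 consecutive days, no medical management | 7 days |
| Recurrent Grade 3 | Permanent stop | No rule |
| Grade 3 seizure | Permanent stop | No seizure-specific rule; the general Grade 3 row allows restart |
| Grade 3 lasting over 7 days | Consider stopping | Consider stopping |
| Grade 4 | Permanent stop | Permanent stop |

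Both tables withhold at Grade 2 and at non-seizure Grade 3. The differences lie in the exit from the hold and in the two permanent-stop rules found only in 14.9.

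**Cases run through both tables**

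1. Grade 2 event improved to Grade 1 today: the 14.17 hold ends; 14.9 does not allow restart.
2. First Grade 3 non-seizure event, at baseline and off medical management for 3 to 6 days: 14.9 allows restart; 14.17 does not.
3. First Grade 3 non-seizure event, settled at Grade 1 but not baseline for 7 days: the 14.17 hold ends; 14.9 does not allow restart.
4. Second Grade 3 event that resolves: 14.9 requires a permanent stop; 14.17 is silent on recurrence, and its Grade 3 row would allow restart.

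Cases 2 and 3 run in opposite directions. At Grade 3, 14.9 is stricter on recovery level and 14.17 on time. At Grade 2, 14.9 is stricter on both.

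**Can the time difference move a dose?** In Cycle 1, doses fall on days 1, 8 and 15, with a window of ±1 day on days 8 and 15. Suppose a Grade 3 non-seizure event after day 1 is back at baseline and off management on day 4.

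- 14.9: 4 + 3 = day 7, in time for day 8.
- 14.17: 4 + 7 = day 11, past day 8 and past the window limit of 8 + 1 = day 9. Counting day 4 as the first day still gives day 10.

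From Cycle 2, doses are 21 days apart. For a patient back at baseline, the time rules then disagree about an on-time dose only if recovery falls at least 3 but fewer than 7 days before it, a span of 7 - 3 = 4 days.

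**Does other text settle it?** No. Section 5.3 names 14.9 without ranking the appendices. It also gives a general restart threshold for non-hematologic events of Grade 1 or lower, with no minimum time, which is a third standard. A footnote in 14.17 sends the reader to *Delayed or Missed Doses* for restart guidance, and no section with that title appears in the supplied text.

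**The case against.** The best case against is that a careful reader can avoid the conflict. Section 5.3 leads to 14.9 alone. Table 16 is permissive while 14.17 sets a floor, so meeting the stricter element of each satisfies both. Principal Investigator approval under the Table 16 footnote would also limit divergent practice. These points reduce the practical risk, but nothing instructs the reader to combine the tables, 14.17 is not marked as subordinate, and it carries no approval requirement of its own.

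Several stronger readings are tempting and are not supported:

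- **That Grade 3 is a choice between 3 and 7 symptom-free days.** The 7 days in 14.17 may be spent at Grade 1, so they need not be symptom-free.
- **That 14.17 is the stricter table on duration.** This holds only at Grade 3.
- **That after a Grade 3 seizure the tables differ by up to 9 of 10 doses** (3 in Cycle 1 plus 7 in Cycles 2-8 makes 10, with 9 left after day 1). In 14.17, seizure appears only as medication advice for ICANS, repeated at Grade 4 where mosunetuzumab is stopped. That is not a seizure restart rule, and the dedicated seizure row in Table 16 would ordinarily govern. The same caution applies to recurrence: 14.17 is silent, which is a gap and not a contrary instruction.
- **That two sites will treat patients differently.** The documents do not establish more than one site; the ambiguity applies equally between investigators at one site.
- **That event counts or the CR result will shift.** A Grade 2 or higher neurologic event is an AESI whichever appendix is used, and no effect on the CR endpoint is shown.

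**Conclusion.** The concern holds for the restart conditions at Grade 2 and at non-seizure Grade 3. At Grade 2 the contrast is at least 3 days at baseline versus no minimum time at Grade 1 or baseline. At Grade 3 it is at least 3 days at baseline versus at least 7 days at Grade 1 or baseline, and each table permits restart where the other does not. The permanent-stop rules for recurrent Grade 3 events and Grade 3-4 seizures stand in 14.9 without a counterpart in 14.17, a lesser defect that rests on silence.

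This rests on reading 14.17 as covering CTCAE-graded neurologic toxicity in general, which its title and first footnote support, and on no precedence statement existing in the supplied text. The documents give no rate of Grade 2-3 neurologic events on mosunetuzumab, so the number of patients affected and any effect on exposure or Part B entry cannot be sized. The point is a safety-relevant inconsistency that should be corrected, not a threat to the primary analysis.

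**What to change.** Reconcile 14.9 and 14.17 into one table that covers, by grade, recovery level, minimum duration, recurrence and seizure. If both must stay, state which events each governs and which prevails on overlap. Cite the result from Section 5.3, say how it relates to that section's general restart threshold, and either supply the *Delayed or Missed Doses* guidance or remove the reference. Which clinical rule to adopt is for the sponsor to decide; this review takes no position. The cost is protocol wording, with no added procedures.
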